#### **4.2 METHOD OF TREATMENT ASSIGNMENT AND BLINDING**

This is a non-randomized, open label study. All volunteers will receive the same study drug treatment (i.e. a single 100 mg dose of entrectinib).

Volunteers with reduced hepatic function will be assigned to a functional category based on assessments at the Screening visit. Each individual will be categorized according to the Child Pugh system for classifying hepatic impairment ([Table 3](#)) and also according to the National Cancer Institute (NCI) organ dysfunction working group (NCI-ODWG) system ([Table 4](#)).

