**Figure 2: Overview of study design**

The study treatment will be administered orally as 1 x 100 mg F06 capsule, and given with approximately 240 mL of water within 30 minutes after consumption of a standardized meal.

Blood samples for measurement of plasma concentrations entrectinib and its active metabolite M5 will be collected before and at intervals up to 144 hr after study drug dosing. In addition, samples will be taken for ex vivo measurement of plasma protein binding. Safety and tolerability will be monitored by clinical and laboratory assessments at intervals throughout the study.

Study participants will be resident in the study center from Day -1 until at least Day 3, although the timing of admission and discharge is at the discretion of the Investigator and individuals may remain resident until Day 7. Volunteers will also have ambulatory study center visits at Screening and Follow-up, and Days 4, 5 and 7 as appropriate.

*Patients who do not meet the criteria for participation in this study (screen failure) cannot be re-screened. The investigator will record reasons for screen failure in the screening log (see Section 4.5.1).*

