##### **Additional criteria for Volunteers with hepatic impairment**

8. Mild, moderate or severe hepatic dysfunction (i.e. Child-Pugh A, B or C, NCI-ODWG Mild, Moderate or Severe) arising from cirrhosis of the liver as the result of parenchymal liver disease. Cirrhosis should be documented by relevant laboratory test results and medical history, including confirmation of the diagnosis by liver biopsy, hepatic ultrasound, computerized tomography (CT) scan or magnetic resonance imaging (MRI) scan.
9. Stable hepatic function. Stable hepatic function is defined as no recent (i.e. within the preceding 14 days) clinically significant change in disease status according to the Investigator's clinical judgment (e.g., no worsening of clinical signs of hepatic impairment, or no worsening of total bilirubin or prothrombin by more than 50%).

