**Table 3: Child-Pugh scoring system for assessment of hepatic dysfunction**

	Score		
	1	2	3
Encephalopathy grade	0	1 or 2	3 or 4
Ascites	Absent	Slight	Moderate
Serum bilirubin (mg/dL)*	<2	2 to 3	>3
Serum albumin (g/dL)†	>3.5	2.8 to 3.5	<2.8
Prothrombin time (seconds prolonged)	<4	4 to 6	>6

Individuals are assigned a score for each parameter, and the sum of these scores is used as the basis for classification of clinical severity:

- 5 to 6 points – mild hepatic impairment (Child-Pugh A)
- 7 to 9 points – moderate (Child-Pugh B)
- >9 points – severe (Child-Pugh C).

Source: [1]

\* Corresponding bilirubin values in SI units: <34.2, 34.2 to 51.3, >51.3 µmol/L

† Corresponding albumin values in SI units: >35, 28 to 35, <28 g/L

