## **6. STATISTICAL CONSIDERATIONS AND ANALYSIS PLAN**

### **6.1 DETERMINATION OF SAMPLE SIZE**

It is planned that approximately 24 volunteers will be enrolled, with a target of six in each hepatic function group. The actual number enrolled will be determined by the Sponsor during the study from review of emerging data to ensure that at least six individuals are recruited in each hepatic function group for both classification systems, i.e. additional volunteers will be recruited if differences between the two categorization systems mean that there are fewer than six evaluable individuals in any hepatic function analysis group. Volunteers who withdraw from the study before Day 7 may also be replaced to ensure that at least six volunteers in each group have evaluable pharmacokinetic data.

No formal sample size calculations were performed. Six volunteers per group is consistent with recommendations in US and European regulatory guidelines [3, 4]. Based on the observed variability in entrectinib exposure parameters in previous clinical studies (e.g.  $AUC_{inf}$  CV% 9-34% from F06 capsules in healthy volunteers under fed conditions) six volunteers per group is considered appropriate to estimate the magnitude of the effect of hepatic impairment on entrectinib pharmacokinetic parameters.

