### **6.4 SAFETY ANALYSES**

The safety analysis population will consist of all volunteers who received one dose of study drug, with volunteers grouped according to hepatic function category.

All verbatim AE terms will be mapped to Medical Dictionary for Regulatory Activities (MedDRA) thesaurus terms, and AE severity will be graded according to NCI CTCAE v5.0.

Safety will be assessed by a review of AEs, vital signs, clinical laboratory assessments, and ECGs. Adverse events will be summarized by hepatic function group. Duplicate summaries will be presented for the Child Pugh and NCI-ODWG systems for classifying hepatic function. Clinical laboratory assessments, vital signs (including oral temperature,

respiratory rate, and supine blood pressure and pulse rate), and ECGs will be listed by volunteer and scheduled time. Changes from baseline and the incidence of out-of-reference range values will be derived as appropriate.

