### **9.2 PROTOCOL DEVIATIONS**

The Investigator should document and explain any protocol deviations. The Investigator should promptly report any deviations that might have an impact on volunteer safety and data integrity to the Sponsor and to the IRB/EC in accordance with established IRB/EC policies and procedures. The Sponsor will review all protocol deviations and assess whether any represent a serious breach of Good Clinical Practice guidelines and require reporting to health authorities. As per the Sponsor's standard operating procedures, prospective requests to deviate from the protocol, including requests to waive protocol eligibility criteria, are not allowed.

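### Does the lack of an NCI-ODWG class for a cirrhotic volunteer with normal bilirubin and AST leave eligibility, the planned 24 or the duplicate analyses in trouble?

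*Combined protocol and SAP*

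**What the plan says.** Inclusion criterion 8 (Section 4.1.1) asks for "Mild, moderate or severe hepatic dysfunction (i.e. Child-Pugh A, B or C, NCI-ODWG Mild, Moderate or Severe) arising from cirrhosis of the liver". The two systems are separated by a comma, with neither *and* nor *or* between them. Section 4.2 then places each impaired volunteer in a Child-Pugh category "and also according to the National Cancer Institute (NCI) organ dysfunction working group (NCI-ODWG) system", and Section 3.3.2 describes the two systems as running in parallel.

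On numbers, Section 6.1 says: "It is planned that approximately 24 volunteers will be enrolled, with a target of six in each hepatic function group". It lets the Sponsor set the actual number from emerging data and adds volunteers when disagreement between the systems leaves "fewer than six evaluable individuals in any hepatic function analysis group".

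On analysis, Section 6.5 compares each impaired group with the control group of normal hepatic function, once per system. It lists a Normal group under each system but defines neither. Section 6.4 defines the safety population as "all volunteers who received one dose of study drug, with volunteers grouped according to hepatic function category", with duplicate adverse event summaries for the two systems.

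Two rules make a screening decision final. Section 3.1 says: "Patients who do not meet the criteria for participation in this study (screen failure) cannot be re-screened". Section 9.2 adds that prospective requests to deviate, "including requests to waive protocol eligibility criteria, are not allowed".

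**The concern.** A cirrhotic volunteer with bilirubin and AST both at or below ULN has a Child-Pugh class but falls outside Table 4. Criterion 8 can then be read in two ways.

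- **An impaired class is needed in both systems.** The volunteer is a screen failure, and the Child-Pugh groups contain only people with raised bilirubin or AST. Nothing in Sections 2.3, 3.3.2 or 6.5 says so.
- **One system is enough.** The volunteer is dosed and counts toward a Child-Pugh group, but has no place among the NCI-ODWG impaired groups. Six per group in both systems can then not be had from 24 people.

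At stake would be the population behind the primary Child-Pugh Mild ratio, the number of people dosed in a study without therapeutic benefit (Section 1.2.2), and where such volunteers appear in the NCI-ODWG tables. A careless analyst might also place them in the undefined Normal NCI-ODWG group and dilute the reference.

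**Working it through.** **1. Which volunteers have no class?**

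Table 3 has five items scored from 1, so the lowest total is 5 × 1 = 5, which is class A. With encephalopathy above grade 2 excluded, the highest possible total is 2 + 4 × 3 = 14. Every score from 5 to 14 has a class.

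Table 4 works out as follows:

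| Bilirubin | AST ≤ ULN | AST > ULN |
|---|---|---|
| ≤ ULN | no class | Mild (B1) |
| > 1 to 1.5 × ULN | Mild (B2) | Mild (B2) |
| > 1.5 to 3 × ULN | Moderate | Moderate |
| > 3 × ULN | Severe | Severe |

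Exactly one cell is empty. If a bilirubin at or below ULN scores 1 point in Table 3 (an assumption about the laboratory's range), such a volunteer can score 5 to 12 and so can be Child-Pugh A, B or C.

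**2. The planned number.** Four groups of six: 4 × 6 = 24. The plan's figure is reproduced.

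**3. The floor with k unclassified volunteers.** Let N be the number of impaired volunteers. The three NCI-ODWG impaired groups need N − k ≥ 18, so N ≥ 18 + k. With six controls the total is at least 24 + k: 25, 26, 27 for k = 1, 2, 3. If the Severe group is not opened, which Sections 3.1, 4.6.2 and 6.6 allow, it is 12 + k + 6 = 18 + k.

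**4. A floor is not an increment.** Suppose 18 volunteers split 6/6/6 by NCI-ODWG but 4/6/8 by Child-Pugh. Two more Child-Pugh A volunteers are needed in any case, giving 18 + 2 + 6 = 26. If those two have no NCI-ODWG class, k = 2 and the floor is also 24 + 2 = 26. Nobody extra is dosed because of them.

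**5. How often (assumed; the documents give no frequency).** If a share q of Child-Pugh A volunteers is unclassified, the chance of at least one among six is 1 − (1 − q)^6:

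| q | Chance of at least one | Mean k = 6q |
|---|---|---|
| 0% | 0% | 0 |
| 10% | 47% | 0.6 |
| 30% | 88% | 1.8 |
| 50% | 98% | 3.0 |

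**6. How far the Child-Pugh Mild ratio could differ between readings (assumed).** If unclassified volunteers have r times the exposure of other Child-Pugh A volunteers and k of six are unclassified, the ratio is multiplied by r^(k/6):

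| r | k = 1 | k = 2 | k = 3 |
|---|---|---|---|
| 1.0 | 1.00 | 1.00 | 1.00 |
| 0.8 | 0.96 | 0.93 | 0.89 |
| 0.67 | 0.94 | 0.88 | 0.82 |

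An illustrative ratio of 1.50 would become 1.50 × 0.82 = 1.23 at the extreme. For scale, the 90% CI factor with six per group and 20 degrees of freedom is exp(t × σ × √(2/6)), with t = 1.725 and σ = √ln(1 + CV²). Using the CV range in Section 6.1, it is 1.09 at CV 9% (σ = 0.0898) and 1.39 at CV 34% (σ = 0.331). All the shifts lie inside the interval at CV 34% (1/1.39 = 0.72). At CV 9% (1/1.09 = 0.92) the three largest, 0.89, 0.88 and 0.82, do not. They are differences between two populations, each of which can be analysed validly.

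**7. Does any analysis break?**

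- Sections 2.3, 3.3.3 and 6.5 compare with a control group of normal hepatic function.
- Section 3.1 enrols those controls separately and matches them.
- Inclusion criterion 6 bars anyone with a history of clinically significant hepatic dysfunction from that group. A cirrhotic volunteer therefore has no route into the reference under either system.
- The Child-Pugh ratios and safety summaries include every dosed impaired volunteer.
- The regressions of exposure on hepatic measures, also a primary endpoint, do not depend on a Table 4 class.
- Only the NCI-ODWG summaries need a place for the k people.

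**The case for a change.** The best argument for acting is that the remedy is cheap and the ambiguity cannot be undone: one word in criterion 8 decides whether a person is dosed, and a screen failure cannot be reversed. Section 6.1 authorises more recruitment but does not say who is eligible. The Normal NCI-ODWG label is undefined, and because Table 4 defines impairment, someone outside it could be called normal. The reading also settles which cirrhotic population the Child-Pugh Mild ratio describes.

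Part of this stands. Criterion 8, Table 4 and the Normal NCI-ODWG label do not fit together neatly, and a clarifying note to sites would do no harm. The rest is weaker. Sections 4.2 and 3.3.2 expect both systems to apply to each impaired volunteer, which fits the reading that adds nobody, though they do not settle it. The finality rules apply equally to every criterion. Pooling cirrhotic volunteers with healthy controls runs against the comparator stated in Section 6.5, and the total would still be at least 24 + k, because the Child-Pugh analysis needs its own six controls. Inconsistent screening is possible but conjectural, and it would be visible because Section 6.4 lists laboratory results by volunteer.

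**Conclusion.** No change follows. This is missing detail that an analyst would fill sensibly: keep the matched controls as the reference in both systems, use a volunteer without an NCI-ODWG class in the Child-Pugh analyses and the regressions, and show that volunteer separately in the NCI-ODWG tables. No stated number is wrong, because 24 is approximate and the recruitment rule covers disagreement between the systems.

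The size is a minimum of 24 + k if such volunteers are eligible and the Severe group opens, 18 + k if it does not open, and no addition if both classes are required. Neither k nor the relative exposure of these volunteers can be estimated from the documents, so the frequencies and ratio shifts shown are illustrations that include a case of no effect. Writing down the reading would make the text clearer but would bring no better method and correct no result.

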**Table 3: Child-Pugh scoring system for assessment of hepatic dysfunction**

	Score		
	1	2	3
Encephalopathy grade	0	1 or 2	3 or 4
Ascites	Absent	Slight	Moderate
Serum bilirubin (mg/dL)*	<2	2 to 3	>3
Serum albumin (g/dL)†	>3.5	2.8 to 3.5	<2.8
Prothrombin time (seconds prolonged)	<4	4 to 6	>6

Individuals are assigned a score for each parameter, and the sum of these scores is used as the basis for classification of clinical severity:

- 5 to 6 points – mild hepatic impairment (Child-Pugh A)
- 7 to 9 points – moderate (Child-Pugh B)
- >9 points – severe (Child-Pugh C).

Source: [1]

\* Corresponding bilirubin values in SI units: <34.2, 34.2 to 51.3, >51.3 µmol/L

† Corresponding albumin values in SI units: >35, 28 to 35, <28 g/L

**Table 4: NCI ODWG definitions of hepatic impairment**

	Mild	Moderate	Severe
Total bilirubin	B1: ≤ULN B2: >1–1.5× ULN	>1.5–3× ULN	>3× ULN
AST	B1: >ULN B2: Any	Any	Any

AST, aspartate aminotransferase; ULN, upper limit of normal.

Source: [2]

Assessment of encephalopathy will primarily be based on clinical signs and symptoms as detailed below; an encephalogram is not obligatory for grading of encephalopathy:

- Grade 0: normal consciousness, personality, neurological examination, electroencephalogram
- Grade 1: restless, sleep disturbed, irritable/agitated, tremor, impaired handwriting, 5 cps waves
- Grade 2: lethargic, time-disoriented, inappropriate, asterixis, ataxia, slow triphasic waves
- Grade 3: somnolent, stuporous, place-disoriented, hyperactive reflexes, rigidity, slower waves
- Grade 4: unrousable coma, no personality/behavior, decerebrate, slow 2-3 cps delta activity

Subjects with severe hepatic encephalopathy (Grade >2) are to be excluded from the study (see Section 4.1.2).

#### **4.3 STUDY TREATMENT AND OTHER TREATMENTS RELEVANT TO THE STUDY DESIGN**

The investigational medicinal product (IMP) for this study is entrectinib.

##### **4.3.1 Study Treatment Formulation, Packaging, and Handling**

Entrectinib will be supplied by the Sponsor as 100 mg capsules (F06 formulation) as finished kits / as capsules in bottles. Further information on the formulation and handling of entrectinib is provided in the pharmacy manual.

The lot numbers for the study drugs will be printed on the IMP drug labels.

Study drugs will be stored at controlled room temperature (store below 25°C) under secure conditions. The study drugs will be transferred into the volunteer's dose container by qualified study site employees. Each unit dose container will be appropriately labeled.

##### **4.3.2 Study Treatment Dosage, Administration, and Compliance**

Each volunteer will receive a single 100 mg dose of entrectinib with food. The study treatment will be administered orally as 1 x 100 mg F06 capsule, and given with approximately 240 mL of water within 30 minutes of consumption of a standardized meal.

Cases of accidental overdose or medication error, along with any associated AEs, should be reported as described in Section 5.4.4. This is a single dose study and dose modification or treatment interruption is not possible. Guidelines for clinical management of individuals who experience AEs are provided in Section 5.1.

##### **4.3.3 Investigational Medicinal Product Accountability**

All IMPs required for completion of this study (entrectinib) will be provided by the Sponsor where required by local health authority regulations. The study site will acknowledge receipt of IMPs supplied by the Sponsor by returning the appropriate documentation form to confirm the shipment condition and content. Any damaged shipments will be replaced.

IMPs will either be disposed of at the study site according to the study site's institutional standard operating procedure or be returned to the Sponsor (if supplied by the Sponsor) with the appropriate documentation. The site's method of destroying Sponsor-supplied IMPs must be agreed to by the Sponsor. The site must obtain written authorization from the Sponsor before any Sponsor-supplied IMP is destroyed, and IMP destruction must be documented on the appropriate form.

Accurate records of all IMPs received at, dispensed from, returned to, and disposed of by the study site should be recorded on the Drug Inventory Log.

#### **4.3.4 Continued Access to Entrectinib**

Currently, the Sponsor does not have any plans to provide entrectinib to volunteers who have completed the study.

### **4.4 CONCOMITANT THERAPY, PROHIBITED FOOD AND ADDITIONAL RESTRICTIONS**

#### **4.4.1 Concomitant Therapy**

Concomitant therapy consists of any medication (e.g., prescription drugs, over-the-counter drugs, vaccines, herbal or homeopathic remedies, nutritional supplements) used by an individual in addition to protocol-mandated treatment from 7 days prior to study drug treatment to the end of the study. All such medications should be reported to the Investigator and recorded on the eCRF.

Concurrent administration of drugs used to manage hepatic dysfunction and related disorders are permitted providing there has been no alteration to the treatment regimen within one week preceding screening and the dosing regimen is not anticipated to change during the study. Similarly, other medications for chronic conditions (e.g. diabetes, hypertension) are permitted providing the volunteer has been on a stable dose and dosing regimen for at least one month preceding screening. However, use of the following categories of medication are specifically prohibited (see [Appendix 2](#) for examples):

- Moderate or potent inhibitors or inducers of CYP3A enzymes.

#### **4.4.2 Contraception**

Women of childbearing potential must agree to remain abstinent (i.e. refrain from heterosexual intercourse) or use a highly-effective method of contraception (failure rate of <1% per year) throughout the study *and for 5 weeks after the last study treatment*.

Women must refrain from donating eggs during this same period. Examples of contraceptive methods with a failure rate of < 1% per year include bilateral tubal ligation, male sterilization, hormonal contraceptives that inhibit ovulation, hormone-releasing intrauterine devices, and copper intrauterine devices.

A woman is considered to be of childbearing potential if she is postmenarcheal but has not reached a postmenopausal state, and has not undergone surgical sterilization.

Postmenopausal is defined as at least 12 months without a period (i.e., amenorrhea) in a female at least 45 years of age and accompanied by a serum follicle-stimulating hormone [FSH] level judged by the Investigator to be consistent with postmenopausal status in the absence of a reversible medical iatrogenic cause. Surgically sterile is defined as permanently sterile via hysterectomy, bilateral oophorectomy, and/or bilateral salpingectomy by reported medical history and/or medical records.

*Men with female partners of child-bearing potential must agree to remain abstinent (i.e. refrain from heterosexual intercourse) or use *barrier* contraception throughout the study and for 3 months after the last study treatment. Men whose female partners are pregnant must also use barrier contraception throughout the study and for 3 months after the last study treatment to avoid potential exposure of the fetus to the study drug. All men must also refrain from donating sperm during the study and for 3 months after the last study treatment.*

Periodic abstinence (e.g., calendar, ovulation, symptothermal, or postovulation methods) and withdrawal are not acceptable methods of contraception.

For volunteers who are exclusively in same-sex relationships or are abstinent (when this is in line with the preferred and usual lifestyle of the volunteer), contraceptive requirements do not apply. If a volunteer who is in a same-sex relationship or abstinent at the time of signing the ICF becomes engaged in a heterosexual relationship, they must agree to use contraception, as described previously.

The reliability of sexual abstinence should be evaluated in relation to the duration of the clinical trial and the preferred and usual lifestyle of the volunteer. Periodic abstinence (e.g., calendar, ovulation, symptothermal, post-ovulation methods) and withdrawal are not acceptable methods of contraception.

#### **4.4.3 Food**

Volunteers should not consume grapefruit or Seville oranges during the study. During periods of in-patient residency, volunteers will also be required to refrain from using tobacco- or nicotine-containing products (including, but not limited to, cigarettes, e-cigarettes, pipes, cigars, chewing tobacco, nicotine patches, nicotine lozenges, and nicotine gum), abstain from consumption of alcohol, and follow restrictions on consumption of food and beverages containing caffeine/xanthines, according to standard practices for the study center.

While resident in the study center, volunteers will receive a standardized diet at scheduled times that do not conflict with other study-related activities.

#### **4.4.4 Additional Restrictions**

Volunteers should refrain from strenuous exercise from 48 hours prior to admission to the study center and during the period of confinement and will otherwise maintain their normal level of physical activity throughout the entire study (i.e., will not begin a new exercise program or participate in any unusually strenuous physical exertion).

